5.6.3 Withdrawal of informed consent

Patients may voluntarily withdraw consent to participate in the study for any reason at any time. Withdrawal of consent from the study is defined as when a patient:

- Does not want to participate in the study anymore, and
- Does not want any further visits or assessments, and
- Does not want any further study related contacts, and

In this situation, the investigator must make every effort (e.g. telephone, e-mail, letter) to determine the primary reason for the patient's decision to withdraw his/her consent and record this information.

Study treatment must be discontinued and no further assessments conducted, and the data that would have been collected at subsequent visits will be considered missing.

Further attempts to contact the patient are not allowed unless safety findings require communicating or follow-up.

All efforts should be made to complete the assessments prior to study withdrawal. A final evaluation at the time of the patient's study withdrawal should be made as detailed in the assessment table below.

5.6.4 Lost to follow-up

For patients whose status is unclear because they fail to appear for study visits without stating an intention to discontinue or withdraw, the investigator should show "due diligence" by documenting in the source documents steps taken to contact the patient, e.g. dates of telephone

calls, registered letters, etc. A patient cannot be considered as lost to follow-up until the time point of his/her scheduled end of study visit has passed.

5.6.5 Early study termination by the sponsor

The study can be terminated by Novartis at any time for any reason. This may include reasons related to the benefit-risk assessment of participating in the study, practical reasons, or for regulatory or medical reasons (including slow enrollment). Should this be necessary, the patient must be seen as soon as possible and treated as a prematurely withdrawn patient. The investigator may be informed of additional procedures to be followed in order to ensure that adequate consideration is given to the protection of the patient's interests. The investigator will be responsible for informing the Institutional Review Board / Independent Ethics Committee (IRBs/IECs) of the early termination of the trial.

6 Visit schedule and assessments

Table 6-1 and Table 6-2 list all of the assessments and indicate with an "X" when the visits are performed.

Patients must be seen for all visits on the designated day, or as close to it as possible. Missed or rescheduled visits should not lead to automatic discontinuation.

During visits 102 to visit 107, intervals between visits must not exceed 7 +/- 1 day calculated from Visit 101 (Day1), to ensure continuous supply regarding oral medication.

During visits 108 to visit 199, intervals between visits should not exceed 28 +/- 4 days calculated from Visit 101 (Day 1). If the visit has to be scheduled outside this window, an approval from the sponsor has to be collected to ensure continuous supply of oral medication and patient safety regarding s.c. medication.

	Screen	Baseline	Double – Blind Treatment Epoch (Titration)						Double – Blind Treatment Epoch (Maintenance)						Follow Up ²
Visit number ¹	0	1	101	102	103	104	105	106	107	108	109	110	111	199	201
End of Week	-6	-4	0	1	2	3	4	5	6	8	12	16	20	24	28
Day	-42	-28	1	8	15	22	29	36	43	57	85	113	141	169	197
Baseline Phase Completion form		x													
Double-Blind Treatment Phase Completion form														x	
Follow-Up Phase Completion form															x

- 1 – All study visit target dates are to be calculated from the Day 1 visit date and all study procedures for a given visit should be completed on the same day.
- 2 – The Follow-Up Visit is required 8 weeks after last IMP injection (erenumab / corresponding Placebo) for patients who discontinue the study or 4 weeks after V199 for patients who complete the study. The Follow-Up visit can be skipped if any other safety follow up visit occurred 8 weeks after last IMP injection.
- 3 – Including prior prophylactic medication.
- 4 – Includes blood pressure, pulse and temperature.
- 5 – Patient brings to each visit for use at site
- 6 – To be completed during applicable study visits before study drug administration, where applicable.
- 7 – Should also be performed at unscheduled visits.
- 8 – SAEs will be collected after signing of the informed consent through the end of the Follow-Up Epoch (8 weeks after the last IMP injection). Non-serious AEs will be collected after randomization (Visit 101) through the end of the Follow-Up Epoch (8 weeks after the last IMP injection).
- 9 – Study drug is administered by study staff, during the applicable study visits, q.m., s.c..
- 10 – Oral study drug will be dispensed to the patient at the center during the applicable study visit for home application.
- 11 – Sites will access the Interactive Response Technology (IRT) System to register study early termination.
- 12 – Should be additionally performed at any visit if deemed necessary by the investigator due to AEs.
- 13 – Should be performed/registered by the investigator prior to dosing during DBTE.
- TD = Treatment discontinuation; PFS = Prefilled syringe; PSD = Premature subject discontinuation; X = Assessment to be recorded in the source documents and the clinical data base; S = Assessment to be recorded as source documentation only.

Table 6-2 Abbreviated schedule of assessments (ASA) for patients with Treatment Discontinuation (TD)

Visit number	V105-ASA	V108-ASA	V109-ASA	V110-ASA	V111-ASA	V199-ASA	V201-ASA ²
End of Week¹	4	8	12	16	20	24	28
Complete Physical Exam						S	
Brief Physical Exam	S	S	S	S	S		
Weight						X	X
Vital Signs ³	X	X	X	X	X	X	X
Chemistry/Hematology ¹²		X				X	X
Serum Pregnancy						X	
Urine pregnancy	S	S	S	S	S		X
ECG						X	
Clinical Outcomes (eDiary)	eDiary should be maintained						
SF-36 ⁴ (eDiary)	X	X	X	X	X	X	
HIT-6 ⁴ (eDiary)	X	X	X	X	X	X	
C-SSRS	X	X	X	X	X	X	
Concomitant Medications	X	X	X	X	X	X	X
Adverse Events ⁵	X	X	X	X	X	X	X
Serious Adverse Events ⁵	X	X	X	X	X	X	X
Follow Up Phase Completion form							X

1 – All study visit target dates are to be calculated from the Day 1 visit date, and all study procedures for a given visit should be completed in the same day.

2 – The Follow-Up Visit is required for all patients who discontinue study drug early, or complete the study and do not continue commercial drug (if locally available). The Follow-Up visit can be skipped if any other safety follow up visit occurred 4 weeks after V199-ASA or the patient continues commercial drug (if locally available). For assessments please refer to table 6-2.

3 – Includes blood pressure, pulse and temperature.

4 – To be completed during applicable study visits before study drug administration, where applicable

5 – SAEs will be collected after signing of the informed consent through the end of the Follow-Up Epoch. Non-serious AEs will be collected after randomization (Visit 101) through the end of the Follow-Up Epoch (V201-ASA).

12 – Should additionally be performed at any visit if deemed necessary by the investigator due to AEs.

TD = Study treatment discontinuation; PSD = Premature patient discontinuation; X = Assessment to be recorded in the source documents and the clinical data base;

S = Assessment to be recorded as source documentation only.

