5.5.6 Rescue treatments

Patients can continue to use acute migraine medication and non-pharmacological interventions as rescue treatments. These may include both pharmacologic interventions (i.e., treatments for acute attacks such as triptans and NSAID) and non-pharmacologic treatments (e.g., biofeedback, psychotherapy or other locally accepted and endorsed interventions for migraine). Non-pharmacological treatment options may only be used as rescue therapy, if patient has been stable on the specific non-pharmacological treatment 3 months prior to baseline.

Patients discontinued from study drug may only use rescue treatments for their migraine attacks as described above.

Site staff will pre-specify the name, dose strength, and route of administration of the patient's acute headache (rescue) medications in the patient's eDiary. If the patient takes an acute headache medication during aura or to treat a migraine or non-migraine headache, they will select one of the pre-specified medications (or "other" medication) and enter the date of administration, the number of times the medication was taken on that date and number of units taken.

Use of rescue medication must be recorded in the eDiary. The acute headache medications reported in the eDiary also will be collected on the Concomitant medications/Significant non-drug therapies eCRF, but data will include only the drug name, indication, and start and stop dates of overall use (i.e., not the individual administration dates). Relevant non-drug therapies as part of "best supportive care" use should also be recorded in the eCRF.

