5.5.8 Prohibited treatments

Use of the treatments displayed in Table 5-1 is NOT allowed as designated due to the potential confounding of efficacy assessments unless in the context of a different pre-existing condition in stable doses for at least 3 months prior to baseline.

Table 5-1 Prohibited Treatments

Treatment	Prohibition period
All prophylactic treatments targeting the CGRP pathway	Any time before study start and throughout the study
Topiramate	Any time before study start
Valproate/Divalproex	Any time before study start and throughout the study
All oral beta blockers	Within 5 half-lives of the start of the baseline epoch and throughout the study
Flunarizine	
Antidepressants (amitriptyline, venlafaxine, desvenlafaxine)	
Antiepileptics (e.g. gabapentin)	
ACE/ARB (lisinopril, candesartan)	
Botulinum toxin (in the head and/or neck region) for medical treatment	Any time before study start and throughout the study
Botulinum toxin (in the head and/or neck region) for cosmetic treatment	Within 4 months of the start of the baseline epoch and throughout the study
Invasive interventions (e.g., nerve blocks, occipital nerve stimulators, transcranial magnetic stimulation)	Within 1 month of the start of the baseline epoch and throughout the study

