5.6 Study completion and discontinuation

5.6.1 Study completion and post-study treatment

A patient will be considered to have completed the double-blind treatment epoch when the patient has completed Visit 199 in the protocol.

The patient's completion status will be recorded on the appropriate Study Phase Completion eCRF pages.

For all patients tapering off Control-IMP after study completion, an unscheduled visit has to be conducted after finishing the tapering off phase. At this visit, information about Control-IMP compliance, AEs, SAEs and concomitant medications have to be collected.

For all patients a safety follow-up visit (visit 201) should be conducted 4 weeks after the last visit or 8 weeks after the last IMP injection. The information to be collected at this follow up visit is outlined in Table 6-1.

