5.6.2 Discontinuation of study treatment

Discontinuation of study treatment for a patient occurs when study drug is stopped earlier than the protocol planned duration, and can be initiated by either the patient or the investigator.

The investigator must discontinue study treatment for a given patient if, on balance, he/she believes that continuation would negatively impact the risk/benefit of trial participation.

Study treatment must be discontinued under the following circumstances:

- Patient wish
- Pregnancy (see Section 6.5.6 and Section 7.5)
- Use of prohibited treatment as per recommendations in Table 5-1
- Any situation in which study treatment might result in a safety risk to the patient
- Any laboratory abnormalities that in the judgment of the investigator, taking into consideration the patient's overall status, prevents the patient from continuing participation in the study

If discontinuation of study treatment occurs, the patient should NOT be considered withdrawn from the study, and should continue recording in the eDiary as per protocol. Also, patients who discontinued treatment from the double-blind treatment epoch will follow the abbreviated visit schedule until the follow up visit (week 28) is reached (Table 6-2). These visits should be performed with all assessments outlined in Table 6-2. At a minimum, the following data should be collected at clinic visits or via telephone visits:

- new/concomitant treatments
- adverse events / serious adverse events

If the patient cannot or is unwilling to attend any visit(s), the site staff should maintain regular telephone contact with the patient, or with a person pre-designated by the patient. This telephone contact should preferably be done according to the study visit schedule.

Patients who prematurely discontinue the study for any reason should be scheduled for a visit as soon as possible, at which time all of the assessments listed for the final visit (Visit 199) will be performed. At this final visit, the adverse event and concomitant medications should be reconciled on the eCRF. Patients will return for a follow-up visit approximately 8 weeks after their last dose of study medication, and perform the study procedures outlined in Table 6-1.

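### Table 6-2 footnote 2 lets a patient who stopped study drug skip the week 28 safety visit, with no substitute, if on commercial drug; Protocol 3.1 and the matching Table 6-1 footnote allow no such exemption

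*Protocol*

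**What the plan says.** Table 6-2 of the protocol is titled "Abbreviated schedule of assessments (ASA) for patients with Treatment Discontinuation (TD"), so every patient on it has stopped study drug. Footnote 2 is attached to the V201-ASA column (week 28) and has two operative sentences.

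- The first sets the rule: "The Follow-Up Visit is required for all patients who discontinue study drug early, or complete the study and do not continue commercial drug" (where locally available).
- The second gives two grounds for omitting the visit. One is that another safety follow-up visit took place 4 weeks after V199-ASA. The other reads "or the patient continues commercial drug (if locally available"). It is not limited to completers and asks for no replacement contact.

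Footnote 5 of the same table ties adverse event collection to this visit: "Non-serious AEs will be collected after randomization (Visit 101) through the end of the Follow-Up Epoch (V201-ASA").

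Elsewhere:

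- Protocol 3.1 makes a follow-up visit mandatory as routine safety monitoring and names discontinued patients. SAP 1.1 repeats this.
- Table 6-1 footnote 2 permits a skip only where another safety visit occurred.
- Protocol 5.6.2 says that stoppers "will follow the abbreviated visit schedule until the follow up visit (week 28) is reached".
- Protocol 5.6.1 states: "For all patients a safety follow-up visit (visit 201) should be conducted".
- Protocol 5.5.6 states: "Patients discontinued from study drug may only use rescue treatments for their migraine attacks as described above".
- Table 5-1 bars "All prophylactic treatments targeting the CGRP pathway" before and throughout the study.

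**The concern.** Sites are given different rules for the same patient. A site working from 3.1 would hold the week 28 visit for a stopper who has started marketed prophylaxis. A site working from the second sentence of footnote 2 could leave it out and hold nothing in its place.

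The patient to whom the waiver applies is also one for whom the visit is useful: he or she has started an active prophylactic against the rescue-only rule, and V201-ASA is the scheduled point for recording concomitant medication and new non-serious events. The urine pregnancy test has a purpose as well, since exclusion criterion 19 requires contraception for 110 days after study medication stops. SAP 2.1.1.5 analyses adverse events up to the patient's end-of-study date, which SAP 2.1.1.1 defines as the last date of participation, so dropping the final visit can bring that window forward.

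**Working it through.** The plan states no figure on this point. The check is a comparison of texts, plus simple arithmetic on visit timing.

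**1. Is the disagreement about timing?** No. Using target days from the visit schedule, week 28 is 1 + 28 × 7 = day 197; V199 plus 4 weeks is 169 + 28 = day 197; the week 20 injection plus 8 weeks is 141 + 56 = day 197. The only question is whether the visit may be omitted.

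**2. How strongly does each text oppose the waiver?**

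| Text | Commercial-drug exemption? | Force against the waiver |
|---|---|---|
| 3.1 | None; visit mandatory, discontinued patients named | Direct conflict |
| Table 6-1 footnote 2 | None; substitute visit needed | Direct departure in the parallel rule |
| 5.6.2 | None in the text, but it refers to Table 6-2 | Tension |
| Table 6-2 footnote 2, first sentence | On the natural reading, limits completers only | Tension |
| 5.6.1 | None, but names visit 201 and Table 6-1 | Weak for this group |
| 5.5.6 and Table 5-1 | Do not mention the visit | Contradict the waiver's precondition only |

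**3. Can a compliant stopper meet the condition before week 28?** Commercial erenumab is barred by both 5.5.6 and Table 5-1. Commercial topiramate is barred by 5.5.6 alone, because Table 5-1 prohibits it only before study start. Either way the patient would be off protocol.

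**4. What is scheduled at V201-ASA?** Table 6-2 marks 8 rows: weight, vital signs, chemistry/haematology, urine pregnancy test, concomitant medication, adverse events, serious adverse events and the follow-up completion form. Chemistry/haematology appears at V108-ASA, V199-ASA and V201-ASA, so 1 of 3 scheduled samples would go.

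**5. How long is the gap?** 197 − 169 = 28 days.

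**6. How much of the 8-week post-injection period lies in the gap?** Days after V199-ASA = max(0, last injection day + 56 − 169).

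- Day 1: 57 − 169 = −112, so 0
- Day 29: 85 − 169 = −84, so 0
- Day 57: 113 − 169 = −56, so 0
- Day 85: 141 − 169 = −28, so 0
- Day 113: 169 − 169 = 0
- Day 141: 197 − 169 = 28, and 28/56 = 50%

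Only 1 of the 6 possible last-injection days loses any of that period.

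**7. Does the gap reach the endpoints?** At target dates month 6 ends on day 141 + 27 = 168 (SAP 2.1.1.4), so its overlap with days 169 to 197 is 0. The primary endpoint is an AE-related treatment stop within the double-blind epoch, and these patients have already stopped.

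**The case against.** The best defence is that the footnote is an ordinary rule followed by its exceptions. The first sentence says who needs the visit, the second says when it can be left out, and the wording is permissive. The commercial-drug condition in the first sentence can also be read as covering both stoppers and completers, which would make the two sentences agree. Because 5.6.2 refers to Table 6-2, it can be said to take the footnote with it. These arguments have weight, and they are why the internal and 5.6.2 conflicts are put no higher than tension. They do not answer 3.1 or Table 6-1 footnote 2, neither of which refers to Table 6-2.

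One limit on 3.1 should be granted. It times a discontinued patient's visit at 8 weeks after the last injection, and by step 6 this falls on or before day 169 for five of the six last-injection days. For those patients another scheduled visit could meet that timing, so 3.1 bites hardest after a week 20 injection. It still contains no commercial-drug exemption.

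A second defence is that the waiver reaches almost nobody, since a compliant stopper cannot meet its condition. It may simply be wording meant for completers left in a table for stoppers. That stands, and it is why the point is small.

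A reader might go further and infer that follow-up adverse events and concomitant medication are necessarily lost. The documents do not support this. Protocol 5.6.2 sets a minimum of new treatments and adverse events that may be collected by telephone, 7.1 requires detected events to be followed, and 7.1 and Table 6-1 footnote 8 also frame collection by time since the last injection. A reader might also infer a biased safety comparison between arms. The documents give no count of affected patients, so neither the size nor the direction of any imbalance can be worked out.

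**Conclusion.** The point holds in a limited form. Footnote 2 of Table 6-2 contains an operative waiver that conflicts with Protocol 3.1, is absent from the parallel Table 6-1 footnote, and fits poorly with 5.6.2 and with its own opening sentence. It depends on drug use that 5.5.6 does not allow before week 28.

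The consequence is confined to a stopper who is off protocol on commercial prophylaxis, at a site that uses the waiver. That patient misses the week 28 weight, vital signs, chemistry/haematology and urine pregnancy test; new non-serious events over about 28 days may go unrecorded unless the site telephones. SAE reporting is defined by time (7.2.2), the primary and secondary endpoints are unaffected, and the safety analyses are descriptive (SAP 2.8).

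This rests on target visit days and on the natural reading of the footnote's first sentence, though the conflict with 3.1 and Table 6-1 does not need that reading. Severity is the low end of minor; confidence is moderate.

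**What to change.** Delete both commercial-drug clauses from Table 6-2 footnote 2: the completer condition in the first sentence and the waiver in the second. The footnote would then say that the follow-up visit is mandatory for every patient who stops study drug early, and may be omitted only where another safety follow-up visit has taken place 4 weeks after V199-ASA.

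The cost is a wording change to one footnote at the next amendment. It adds no visit or procedure, since V201-ASA is already on the schedule for these patients, and it leaves the analysis plan unchanged.

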6.1 Information to be collected on screening failures

All patients who have signed informed consent but not entered into the next epoch will have the study completion page for the Screening Epoch, demographics, inclusion/exclusion, and serious adverse event (SAE) data collected. Adverse events that are not SAEs will be followed by the investigator and collected only in the source data.

6.2 Patient demographics/other baseline characteristics

Patient demographic and baseline characteristic data will be collected on all patients include: year of birth, age, sex, race, source of patient referral, relevant medical history/current medical condition present before signing informed consent. Where possible, diagnoses not symptoms will be recorded.

Prior headache characteristics and previous headache medication history, including information on the suitability for migraine prophylactics will be collected as part of baseline characteristics.

Investigators will have the discretion to record abnormal test findings on the medical history eCRF whenever in their judgment, the test abnormality occurred prior to the informed consent signature.

6.3 Treatment exposure and compliance

Study medication is administered at the site (test-IMP) or dispensed to the patient (control-IMP) by the investigator or designated study staff as outlined in Table 6-1. This information should be captured in the source document and the eCRF at each visit. All study treatments dispensed and returned must be recorded in the Drug Accountability Log. Site staff will review eDiary compliance and control-IMP compliance (topiramate) with the patient at each visit.

6.4 Efficacy

Efficacy assessments will include:

- Migraine days

The timing and frequency of these assessments are outlined in Table 6-1. Patients will record the efficacy information using the provided eDiary platform. To aid in compliance, it is recommended that the information be completed at the same time every day that is convenient for the patient. Retroactive completion will be allowed up to 48hours prior to the time of completion. Any entries >48 hours will not be allowed and will be considered missing data. Data collected in the eDiary will be normalized to a 28 day period.

